#### 4.4. Secondary Efficacy Endpoints

The secondary efficacy endpoints are as follows:

- The duration of platelet response (months) and total duration of platelet response (months)
- Patients with reduction in the dose of concomitant ITP therapy while maintaining an adequate platelet count (yes/no)

Duration of platelet response will be defined as the length of time from when the patient first achieves a platelet count of at least 50,000/ $\mu$ L until the first of two visits with platelet counts < 50,000/ $\mu$ L that are at least 4 weeks apart without an intervening visit with a platelet count  $\geq$  50,000/ $\mu$ L unrelated to rescue therapy.

Four additional definitions of duration of platelet responses are stated in **Appendix 14.2**

Patients who drop out of the study before achieving a platelet response (i.e., achieving a platelet count of  $\geq$  50,000/ $\mu$ L) will be assigned a value of 0 for this endpoint. Patients who drop out of the study by the time of database lock while still maintaining a platelet response will be censored as of the time of the last platelet measurement prior to dropping out of the study. Similarly, patients who remain in the study by the time of database lock while still maintaining a platelet response will be censored as of the time of the last platelet measurement prior to the time of database lock. For patients who have achieved and are maintaining a platelet response but who have discontinued treatment due to lack of efficacy or to an AE by the time of database lock, duration of platelet response will be defined as the time from first achieving a platelet count of  $\geq$  50,000/ $\mu$ L until discontinuation of treatment.

The total duration of platelet response is defined as the sum of all durations of platelet responses.

Regarding the secondary efficacy endpoint of patients with reduction in the dose of concomitant ITP therapy while maintaining an adequate platelet (yes/no), a patient is said to have reduction while maintaining an adequate platelet count if the date of reduction of dose of concomitant ITP therapy occurs within the span of the duration of a platelet response during the C-935788-049 study and the reduction was not prompted by AE.

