4.3 Secondary Efficacy Endpoints

- The duration of any stable platelet response
- Proportion of subjects in whom a reduction in the dose of concomitant ITP therapy can be achieved while maintaining an adequate platelet count

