7.7.1 Allowed ITP Therapies

Subjects may continue concurrent therapies for ITP that were allowed at entry (ie, glucocorticoids at a dose less than the equivalent of 20 mg prednisone daily, or azathioprine, or danazol). Consideration can be given to tapering the dose of any concomitant ITP medication, in

subjects whose platelet count is stable at $\geq 50,000/\mu\text{L}$. New treatments for ITP may not be added.

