### 4.3. Primary Efficacy Endpoint

**Version 1:** The first version of the primary efficacy endpoint is for the purpose of assessing efficacy among all patients while they are on active treatment in one of the prior studies, in the current extension study, or in both. This version of the primary efficacy endpoint is the achievement and maintenance of a stable platelet response defined as follows:

- 1) Achievement of a platelet count of at least 50,000/ $\mu$ L within 12 weeks of beginning active treatment and
- 2) Achievement of a sustained stable platelet response; defined as no two visits, at least 4 weeks apart, with a platelet count < 50,000/  $\mu$ L, without an intervening visit with a platelet count of  $\geq$  50,000/  $\mu$ L unrelated to rescue therapy, within a period of 12 months following initial achievement of the target platelet count (see above).

The beginning of active treatment may be in the prior study or in the present extension study, depending upon when the patient first received active treatment. Patients who discontinue treatment due to lack of efficacy or to an AE prior to 12 months following achievement of a platelet count of at least 50,000/ $\mu$ L will be considered failures.

**Version 2:** The second version of the primary efficacy endpoint is for the purpose of a within-patient, between-study comparison of fostamatinib and placebo among patients randomized to placebo in either of the prior studies, This version of the primary efficacy endpoint is the achievement and maintenance of a stable platelet response defined as follows:

- 1) Achievement of a platelet count of at least 50,000/ $\mu$ L within 12 weeks of beginning treatment (placebo treatment in the prior study and fostamatinib treatment in the present study) and
- 2) Achievement of a sustained stable platelet response; defined as no two visits, at least 4 weeks apart, with a platelet count < 50,000/  $\mu$ L, without an intervening visit with a platelet count of  $\geq$  50,000/  $\mu$ L unrelated to rescue therapy, within a period of 12 weeks following initial achievement of the target platelet count (see above).

Platelet counts taken within 28 days of rescue therapy will be excluded when determining the value of this endpoint. Patients who discontinue treatment or patients who are rescued prior to 12 weeks following achievement of a platelet count of at least 50,000/ $\mu$ L, will be considered failures.

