## **5.0 STATISTICAL METHODS**

### **5.1 General Considerations**

The statistical analysis for this study will be performed using SAS® version 9.4 or higher. All one-sided statistical tests will be performed at the 0.025 significance level, and all two-sided tests will be performed at the 0.05 significance level, unless otherwise indicated.

Prior study treatment group will refer to the patient's randomized treatment group (fostamatinib or placebo) from the previous study in which the patient participated. Unless otherwise specified.

Analyses will be based on only the data from the present study (C935788-049), except for the baseline value and a few other exceptions (e.g., duration of platelet response, primary efficacy endpoint, and the platelet count by-visit summary).

Data collected in this study will be documented using summary tables and patient data listings. Continuous variables will be summarized using descriptive statistics, specifically the mean, median, 25th percentile (Q1), 75th percentile (Q3), standard deviation, minimum and maximum. Categorical variables will be summarized using frequencies and percentages.

Data listings will be sorted by prior study treatment group and patient ID number. All date fields will be presented in a format of ddmmyyyy (i.e., 01Jan2014) in the listings. All data will be included in the data listings.

As a global note, platelet counts taken within 28 days of rescue therapy will be excluded from any platelet count related analyses.

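### The background-therapy endpoint is decided by the date of the dose cut, so a taper that fails afterwards is still classed as one with the platelet count maintained

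*SAP*

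**What the plan says.** Protocol 4.3 lists this secondary endpoint: "Proportion of subjects in whom a reduction in the dose of concomitant ITP therapy can be achieved while maintaining an adequate platelet count". Neither that section nor protocol 10.4.2 says what maintaining means in practice. Protocol 10.4.2 plans counts, percentages, a 95% Clopper-Pearson interval and a McNemar's test. On when a taper may start, protocol 7.7.1 says "Consideration can be given to tapering the dose of any concomitant ITP medication, in" people with a stable count of 50,000/µL or more.

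SAP 4.4 supplies the working rule, in two parts. The first names the date as the thing to be tested: "a patient is said to have reduction while maintaining an adequate platelet count if the date of reduction of dose of concomitant ITP therapy occurs". The second says where that date has to lie: "within the span of the duration of a platelet response during the C-935788-049 study and the reduction was not prompted by AE". It sets no other condition.

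The span comes from the same section. Its start is given in these words: "Duration of platelet response will be defined as the length of time from when the patient first achieves a platelet count". The threshold is 50,000/µL, and the span ends at the first of two visits below it "that are at least 4 weeks apart without an intervening visit with a platelet count" back at 50,000/µL or more that is unrelated to rescue. SAP 5.1 adds: "As a global note, platelet counts taken within 28 days of rescue therapy will be excluded from any platelet count related analyses".

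For reporting, SAP 10.2.3 plans only a patient-level listing of concomitant ITP use. SAP 3.5 replaces the McNemar's test with that listing and does not mention the counts, percentages or interval.

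**The concern.** The endpoint asks whether background treatment can be reduced with the count held. That can only be answered by what happens after the reduction, and the rule looks at the day of the reduction.

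A taper that causes loss of response comes before the first low visit. If it is made during a response, its date is always inside the span and it always scores as a success. The one failure that the endpoint exists to detect is the one that it cannot register. Protocol 7.7.1 does not fill the gap, because stability there is a condition for starting a taper and not a check on its result.

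At stake is any statement that fostamatinib lets patients reduce background ITP therapy.

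**Working it through.** The documents state no rate, power or sample size for this endpoint, so there is no figure to reproduce. The check is to apply the SAP 4.4 rule, as written, to hypothetical patients.

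**Inputs.** The span start and end are from SAP 4.4 and the 28-day exclusion after rescue is from SAP 5.1. Visits are about monthly (SAP Table 1). Every patient has 60,000, 70,000 and 80,000/µL on Days 30, 60 and 90. The cut is on Day 91, except in case D. For comparison, a 12-week condition is added, borrowed from the Version 2 maintenance period in SAP 4.3: no loss, rescue or return to the earlier dose up to Day 91 + 84 = Day 175.

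| Case | What follows | Span under SAP 4.4 | SAP rule | With 12-week condition |
|---|---|---|---|---|
| A | 30,000 on Day 120, 20,000 on Days 150 and 180 | Day 30 to Day 120 | success | not a success |
| B | 30,000 on Day 120, dose restored Day 121, 65,000 on Day 150, 70,000 on Days 180 and 210 | from Day 30, not ended by Day 210 | success | not a success |
| C | 75,000, 65,000, 70,000, 70,000 on Days 120, 150, 180, 210 | from Day 30, not ended by Day 210 | success | success |
| D | 30,000 on Day 120, cut on Day 125, 20,000 on Day 150 | Day 30 to Day 120 | not a success | not a success |
| E | rescue on Day 118, Day 120 count dropped, 60,000 on Day 150, 55,000 on Day 180 | from Day 30, not ended by Day 180 | success | not a success |

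- **A:** 30 ≤ 91 < 120, so the cut is inside the span although confirmed loss begins at the next visit.
- **B:** one low count does not end a span, and a restored dose plays no part in the rule.
- **D:** later counts do have one effect. The confirmed loss closes the span on Day 120, so a cut on Day 125 is excluded. This never catches a cut that precedes the loss.
- **E:** rescue does not end the main SAP 4.4 span. The Day 120 count is removed, while the Day 150 count is kept because 118 + 28 = 146.

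**Illustration of size (all numbers assumed).** Take 10 apparent successes, of which 0, 2 or 5 do not hold, and n patients on background therapy.

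| n | 10/n | 8/n | 5/n |
|---|---|---|---|
| 30 | 33.3% | 26.7% | 16.7% |
| 50 | 20.0% | 16.0% | 10.0% |
| 70 | 14.3% | 11.4% | 7.1% |

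For n = 30 the exact 95% intervals are 17.3% to 52.8%, 12.3% to 45.9% and 5.6% to 34.7%. The added conditions only remove successes, so for a fixed denominator the error has one direction.

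**The case against.** The strongest reply is that no planned SAP output carries the error. SAP 10.2.3 gives a listing, in which a dose put back up could be seen. SAP 5.1 puts all data in listings, and SAP 12.5 summarises rescue separately. The trial is an open-label extension whose primary objective is safety. All of this stands, and it limits the consequence. It does not repair the rule: SAP 4.4 still defines a yes/no secondary endpoint, protocol 10.4.2 still specifies a proportion with an interval, and SAP 3.5 expressly drops only the McNemar's test.

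Three stronger readings are tempting, and the documents support none of them.

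- A reader might infer that later counts are ignored altogether. Case D shows otherwise.
- A reader might infer that nearly every taper scores as a success. The endpoint is a proportion of subjects, not of tapered subjects. Cuts prompted by an adverse event or made outside a response are excluded, and no taper numbers are given.
- A reader might try to state the share of false successes. With a taper date uniform over an assumed 6-month span, loss within 4 or 12 weeks of the cut has probability 4/26.1 = 15% or 12/26.1 = 46%. With 12 months it is 4/52.2 = 8% or 12/52.2 = 23%. These figures apply only to responses that end in loss. If half of the successes never lose response, 46% becomes 23%. They also count losses that merely follow the cut by chance, and the spans come from nowhere in the documents.

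It is also fair to say that 12 weeks is borrowed. In Version 2 it runs from first reaching the target count, not from a dose cut. The length is for the sponsor to justify.

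**Conclusion.** The concern holds in a limited form. As written, the SAP 4.4 rule misclassifies tapers followed by loss of response, rescue or a return to the earlier dose. This follows from the text and needs no assumption about the data. For a fixed denominator, any rate built on the rule would be too high whenever such a taper occurs. By how much cannot be estimated, because the documents give no number of patients on background therapy, no number of tapers and no outcomes after them. The rates worked out above are illustrations.

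The error matters if the yes/no result is tabulated or quoted. It does not mean that a wrong rate will be reported, since the SAP plans none. It is worth correcting because protocol and SAP disagree on whether a proportion is due.

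**What to change.** In SAP 4.4, keep the present conditions and add a prespecified period after the reduction, for example 12 weeks or another length that the sponsor justifies. Within it, require all of the following:

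- at least one platelet count not excluded for rescue;
- no loss of response, as defined in SAP 4.4, whose first low visit falls in the period;
- no rescue therapy;
- no return to or above the dose held before the reduction.

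Take patients on concomitant ITP therapy at Day 1 of the 049 study as the denominator. Report those with too little follow-up after the cut as a separate not-evaluable category, with a sensitivity analysis that counts them as not successful. Scoring them as failures in the main analysis would confuse the end of observation with failure of the taper. Show the date-only definition as a further sensitivity analysis. Reconcile SAP 10.2.3 with protocol 10.4.2 on whether the proportion and interval are reported.

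The cost is SAP wording and programming on platelet, rescue and concomitant-medication data already collected. No patient's treatment changes. There will be fewer successes, and some late tapers will not be evaluable. After Month 18 visits are every other month, so a 12-week period may hold only one scheduled count. The confirming low visit may then fall outside the period, which is why the condition is tied to the first low visit.

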#### 4.5. Safety Endpoints

The following safety endpoints will be evaluated:

- Adverse events
- Adverse events of interest, including:

- Gastrointestinal (GI) events
  - Nausea
  - Vomiting,
  - Diarrhea as reported by SMQ (v19.1) of non-infectious diarrhea
  - Abdominal pain
- Infection
- Hypertension as reported by SMQ (v19.1)
- Increases in transaminases and/or total bilirubin as defined by SMQ (v19.1) of Hepatic Disorder
- Neutropenia
- Percent change from baseline in lab assessments (hematology, serum chemistry and liver function tests) over time
- Presence of abnormal changes from baseline in laboratory values per Common Terminology Criteria for Adverse Events (CTCAE) criteria V 5.0 (e.g., hematology, chemistry)
- Severity of bleeding according to the IBLS and the WHO bleeding scale
- Change from baseline in vital signs (i.e., systolic /diastolic blood pressures, pulse, temperature) over time
- Post baseline blood pressure categorized based on post baseline systolic and diastolic blood pressure values.

#### **4.6. Other Endpoints**

- Change and percent change from baseline in Karnofsky Performance Status (KPS) over time
- Change from baseline in Short form-36 (SF-36) over time

#### **4.7. Pharmacokinetic Endpoints**

Characterization of the PK profile of R406 (the active metabolite of fostamatinib) including Cmax, AUC, and Tmax in a subset of subjects with ITP.

## **5.0 STATISTICAL METHODS**

### **5.1 General Considerations**

The statistical analysis for this study will be performed using SAS® version 9.4 or higher. All one-sided statistical tests will be performed at the 0.025 significance level, and all two-sided tests will be performed at the 0.05 significance level, unless otherwise indicated.

Prior study treatment group will refer to the patient's randomized treatment group (fostamatinib or placebo) from the previous study in which the patient participated. Unless otherwise specified.

Analyses will be based on only the data from the present study (C935788-049), except for the baseline value and a few other exceptions (e.g., duration of platelet response, primary efficacy endpoint, and the platelet count by-visit summary).

Data collected in this study will be documented using summary tables and patient data listings. Continuous variables will be summarized using descriptive statistics, specifically the mean, median, 25th percentile (Q1), 75th percentile (Q3), standard deviation, minimum and maximum. Categorical variables will be summarized using frequencies and percentages.

Data listings will be sorted by prior study treatment group and patient ID number. All date fields will be presented in a format of ddmmyyyy (i.e., 01Jan2014) in the listings. All data will be included in the data listings.

As a global note, platelet counts taken within 28 days of rescue therapy will be excluded from any platelet count related analyses.

### **5.2 Adjustments for Covariates**

No adjustments for covariates will be made.

### **5.3 Handling of Dropouts and Missing Data**

No imputation will be performed for missing data

### **5.4 Interim Analyses and Data Monitoring**

An interim analysis was performed for purposes of inclusion in the New Drug Application for fostamatinib.

### **5.5 Multicenter Study**

This is a multicenter study. Up to 150 patients will be enrolled at multiple sites. No adjustments for site will be made in the statistical analyses.

### **5.6 Multiple Comparisons / Multiplicity**

No adjustments for multiple comparisons/multiplicity will be made.

### **5.7. Examination of Subgroups**

Platelet count will be summarized by 047/048 primary efficacy endpoint responder status and 049 primary efficacy endpoint version 2 responder status for 047/048 placebo patients, and for 049 primary efficacy endpoint **Version 1** responders (defined in **Section 4.3**).

Maximum systolic and diastolic blood pressure on active treatment (post-baseline of the present study) will be summarized by baseline use of anti-hypertensives.

Interventions required to manage hypertension will also be summarized by baseline use of anti-hypertensives and by prior study treatment group (fostamatinib and placebo) and overall.

### **5.8. Definition of Baseline Measurements**

For the summary of baseline characteristics of present study, the baseline characteristics used for summary are defined in **Section 4.1** and **4.2**.

For the calculation of change from baseline, the baseline value is defined as the last measurement for the corresponding variable prior to the first dose of fostamatinib in Study C-935788-047 or C-935788-048 (for fostamatinib patients in the previous study) or the present study (for placebo patients in the previous study).

## **6.0 ANALYSIS POPULATIONS**

### **6.1. Treated Population**

The Treated Population will include all enrolled and treated patients in the present study. All efficacy and safety analyses will be performed on the Treated Population.

## **7.0 PATIENT DISPOSITION**

The number of patients signing the informed consent, screen failures, and patients in the Treated Population will be presented. The numbers and percentages of patients who discontinued from the study at the time of database lock, along with the reason for discontinuation, will be also be presented.

## **8.0 DEMOGRAPHIC, BASELINE CHARACTERISTICS, ITP HISTORY AND PREVIOUS PROCEDURES**

The demographic/baseline characteristics and ITP history/previous procedures are defined in **Section 4.1** and **4.2**, respectively. Descriptive statistics will be presented for the continuous variables. Frequencies and percentages will be presented for the categorical variables.

## **9.0 STUDY DRUG DISPENSING, COMPLIANCE, AND EXPOSURE**

The dose level of fostamatinib dispensed and changes in the dose level dispensed will be summarized by visit using counts and percentages. Changes in the dose level dispensed include increase in dose level dispensed and decrease in dose level dispensed, respectively as follows:

- Increase in dose level dispensed, including change from 100 mg bid to 150 mg bid, change from 150 mg qd to 100 mg bid and change from 100 mg qd to 150 mg qd, respectively
- Decrease in dose level dispensed including change from 150 mg bid to 100 mg bid, change from 100 mg bid to 150 mg qd and change from 150 mg qd to 100 mg qd, respectively

The expected number of doses, actual number of doses, number of missed doses, and percent compliance will be summarized by time interval and overall using descriptive statistics. Percent compliance is defined as the actual number of doses (tablets) the patient took during the time period divided by the total number of tablets expected to be taken, multiplied by 100.

The duration of dosing of fostamatinib and the mean total daily dose will be summarized using descriptive statistics and displayed in waterfall plots. In addition, the number and percentage of following subgroups of patients will be presented

- Patients with at least 3 months of duration of dosing of fostamatinib
- Patients with at least 6 months of duration of dosing of fostamatinib
- Patients with at least 12 months of duration of dosing of fostamatinib
- Patients with at least 18 months of duration of dosing of fostamatinib
- Patients with at least 24 months of duration of dosing of fostamatinib

The number and percentage of patients with at least one dose interruption with duration less than or equal to 2 days, greater than 2 days, and of unknown duration, and the number and percent of patients with a dose interruption followed by early termination, with at least one dose interruption due to adverse events, and with any dose interruption will be presented. Among patients with at least one dose interruption, the total number and mean number per patient of dose interruptions with duration less than or equal to 2 days, greater than 2 days, and of unknown duration, and the total number and mean number per patient of dose interruptions due to adverse events will be presented.

## 10.0 EFFICACY ANALYSES

### 10.1 Primary Efficacy Endpoint

#### 10.1.1 Version 1

The first version of the primary efficacy endpoint is defined in **Section 4.4** and applies for all patients entering C-935788-049 study. It will be summarized using counts and percentages, together with a 95% exact (Clopper-Pearson) confidence interval for the true percentage of Version 1 responders.

#### 10.1.2 Version 2

The second version of the primary efficacy endpoint is defined in **Section 4.4** and applies for all patients randomized to placebo in either C-935788-047 or C-935788-048 studies and entering C-935788-049 study.

These endpoints will be summarized based on a shift table (**Table 3** below) presenting shifts in responder status from placebo treatment in the C-935788-047 or C-935788-048 studies to fostamatinib treatment in the C-935788-049 study using counts and percentages, together with 95% exact (Clopper-Pearson) confidence intervals for the true percentage of Version 2 responders. In addition, the following hypothesis test will be conducted:

$H_0: P_{01} - P_{10} = 0$  vs.  $H_a: P_{01} - P_{10} \neq 0$ ,

Where  $P_{01}$  denotes true proportions of non-responders from placebo patients in C-935788-047 or C-935788-048 studies who become Version 2 responders in C-935788-049 study and

$P_{10}$  denotes true proportions of stable responders from placebo patients in C-935788-047 or C-935788-048 studies who become Version 2 non-responders in C-935788-049 study.

here  $P_{01}$  and  $P_{10}$  are estimated by  $\frac{c}{a+b+c+d}$  and  $\frac{b}{a+b+c+d}$ , respectively, where a, b, c and d are number of patients as defined in **Table 3** below

**Table 3.** Shift of Response Status For Version 2 Response

Placebo Patients in C-935788-047 or C-935788-048 Studies Who Entered C-935788-049 Study

		Version 2 Responders in C-935788-049 Study		
		Yes	No	Total
Stable Responder in C-935788-047 or C-935788-048 Studies	Yes	a	b	a+b
	No	c	d	c+d
	Total	a+c	b+d	a+b+c+d

The p-value of the null hypothesis test for  $H_0: P_{01} - P_{10} = 0$  will be calculated using a 2-sided exact McNemar's test with a significance level of 0.05. The 95% confidence intervals for the difference in proportion of  $P_{01} - P_{10}$  will be calculated using normal approximation method.

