Subjects who discontinue treatment due to lack of efficacy or to an AE prior to 12 weeks following achievement of a platelet count of at least 50,000/ μ L, will be considered failures. The null and alternative hypotheses for the comparison of fostamatinib vs. placebo are as follows:

$$H_0: p_F = p_P \quad \text{vs.} \quad H_1: p_F \neq p_P$$

where p_F and p_P denote the true proportions achieving and maintaining a stable platelet count for fostamatinib and placebo, respectively. The null hypothesis will be tested using a 2-sided

McNemar's test conducted with a significance level of 0.05. This analysis will be performed for the Treated and Per Protocol populations.

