**Figure 1: Study Design**

\*At Month 1 subjects receiving fostamatinib 100 mg *bid* should have the dose escalated to fostamatinib 150 mg *bid* if the platelet count is <50,000/μL.

Eligible subjects include subjects from Study C-935788-047 or C-935788-048 who have completed the Week 24 evaluation or who discontinue early (starting at Week 12) due to lack of response. Subjects must meet the Inclusion/Exclusion criteria listed in Section 6.1 and Section 6.2 of the protocol to be eligible to participate in the study. Subjects designated as responders (defined as platelet count  $\geq 50,000/\mu\text{L}$ ) at the time of rollover will continue in the extension study at their current Study C-935788-047 or C-935788-048 dose and regimen. Subjects who

enter the extension study as non-responders (defined as platelet count < 50,000/ $\mu$ L) will be allocated to fostamatinib 100 mg PO bid regardless of their dose and regimen in the prior study. All subjects will receive open-label fostamatinib. Subjects will remain blinded to their treatment assignment (active or placebo) from Study C-935788-047 or C-935788-048.

At Month 1, subjects receiving fostamatinib 100 mg PO *bid* should have the dose escalated to fostamatinib 150 mg PO *bid* if platelet count < 50,000/ $\mu$ L and the study drug is well tolerated (refer to Section 7.2.1 of the protocol). Conversely, the dose may be reduced at any time to a dose as low as fostamatinib 100 mg PO *qd* if dose limiting AEs are observed as defined by the extension study protocol (see Section 7.2.2 and Appendix 1, Appendix 2, Appendix 3, and Appendix 4 of the protocol).

A schedule of study procedures for this study is presented in **Table 1**.

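### Does SAP Table 3 score the placebo period by a different response rule from the fostamatinib period?

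*SAP*

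**What the plan says.** Protocol 10.4.1.2 defines the Version 2 endpoint once and tests p_F = p_P, where these "denote the true proportions achieving and maintaining a stable platelet count for fostamatinib and placebo, respectively".

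SAP 4.3 repeats that definition as a stable platelet response. A count of at least 50,000/µL must be reached within 12 weeks of starting treatment, with both treatments named ("placebo treatment in the prior study and fostamatinib treatment in the present study"), and the response must then hold for 12 weeks. It adds: "Platelet counts taken within 28 days of rescue therapy will be excluded when determining the value of this endpoint". Discontinuation or rescue before the 12 weeks are complete counts as failure.

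SAP 10.1.2 turns this into a shift table, "presenting shifts in responder status from placebo treatment in the C-935788-047 or C-935788-048 studies" to fostamatinib in 049, under the title "Shift of Response Status For Version 2 Response". The columns are Version 2 responders in 049 (yes/no). The rows are stable responders in 047 or 048 (yes/no). P01 denotes the "true proportions of non-responders from placebo patients in C-935788-047 or C-935788-048 studies who become Version 2 responders in C-935788-049 study" and is estimated by c/(a+b+c+d). P10 denotes the "true proportions of stable responders from placebo patients in C-935788-047 or C-935788-048 studies who become Version 2 non-responders in C-935788-049 study" and is estimated by b/(a+b+c+d).

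Both 10.1.1 and 10.1.2 send the reader to Section 4.4 for the definition, but it stands in Section 4.3.

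**The concern.** A within-patient comparison is fair only if one rule scores both periods. In SAP 10.1.2 the column carries the Version 2 name and the row does not. The row term, stable responder, has no definition of its own. P10 starts from stable responders and P01 from non-responders. The one place where the SAP defines non-responders is Section 3.1, for patients who "enter the extension study as non-responders (defined as platelet count < 50,000"/µL). That is a single count at roll-over, and it can disagree with Version 2. A placebo patient below 50,000/µL through Week 12 and at or above it at Week 24 fails Version 2 but is a responder at roll-over.

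SAP 5.7 and 10.3 also classify the same placebo patients by the primary endpoint of 047/048, as a status separate from Version 2. A reader could take the Table 3 row to mean that.

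The stake is the only fostamatinib-placebo test left in the readable SAP, because Section 3.5 drops the McNemar test on concomitant ITP therapy. If the rows followed another rule, the estimate and its interval would mix a treatment difference with a difference between definitions. With few discordant pairs the p-value could move too. With assumed counts b = 0, c = 8 the exact two-sided p is 2 × (1/2)^8 = 0.0078. With b = 1, c = 7 it is 2 × (8 + 1)/2^8 = 0.0703.

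**Working it through.** The plan has no figure to reproduce: neither document gives a sample size calculation, expected cell counts or the number of placebo roll-overs. The inputs are the definitions in SAP 4.3, the cells and estimators in SAP 10.1.2, and the protocol's hypothesis.

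**1. What the test estimates.** With n = a+b+c+d,

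P01 - P10 = c/n - b/n = (a+c)/n - (a+b)/n.

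The first margin is the proportion of Version 2 responders on fostamatinib. The second is the proportion of responders on placebo. If the row is scored by Version 2, this is the protocol's p_F - p_P. Illustration with assumed cells a=1, b=1, c=7, d=36 (n=45): (7-1)/45 = 13.3 points, and 8/45 - 2/45 = 17.8% - 4.4% = 13.3 points.

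**2. Are the two placebo-period terms complements?** P01 is estimated from c, and c lies in the row where stable responder is No. The formula therefore fixes non-responder in P01 as not a stable responder. The roll-over definition in SAP 3.1 plays no part. It decides the starting dose, and SAP 3.5 says that roll-over responders did not have to be stable responders. The SAP itself keeps the two statuses apart, so the roll-over disagreement described above does not bear on Table 3.

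**3. Which rule scores the row?**

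| Place | What it indicates |
|---|---|
| SAP 4.3 | Version 2 is defined as a stable platelet response, scored on placebo in the prior study and on fostamatinib in this one. Stable responder is its natural short form. |
| SAP 10.1.2, opening and lead-in | Starts from the Version 2 endpoint and summarises it by shifts in responder status from placebo to fostamatinib. |
| Table 3 title | Puts the whole table, not one axis, under Version 2. |
| SAP 5.1 | Limits analyses to 049 data but excepts the primary efficacy endpoint, so parent-study data may be used. It also makes the 28-day rescue exclusion global. |
| SAP 5.7 and 10.3 | Where the 047/048 primary endpoint is meant, it is named in full. Table 3 does not use that name. |

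**4. Can the rule be scored on placebo?** It needs at most 12 + 12 = 24 weeks, and the parent studies run to a Week 24 evaluation. A patient who leaves earlier for lack of response, from Week 12 on, fails either because 50,000/µL was not reached within 12 weeks or because treatment stopped before 12 weeks of maintenance.

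**5. Does the wrong section reference mislead?** Section 4.4 holds the secondary endpoints and contains no other Version 2 rule. A reader sent there finds no competing definition and has only to turn back one section.

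**6. Size, if a row were wrong.** Moving one patient from row No to row Yes (c to a, or d to b) lowers P01 - P10 by exactly 1/n. For an assumed n of 30, 45 or 60 this is 100/30 = 3.3, 100/45 = 2.2 or 100/60 = 1.7 points. This holds for any 2x2 table. It does not show that any patient is in the wrong row.

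**The case for a change.** The strongest opposing case is that one rule is inferred and not stated. SAP 3.2 speaks of a stable platelet response achieved in 047 or 048, so the row label could be shorthand for a parent-study outcome, and the parent definitions are not in these documents. Nor does the silence of SAP 3.5 on Version 2 scoring settle the matter. SAP 4.3 widens the protocol's failure rule from discontinuation for lack of efficacy or an AE to any discontinuation or rescue, and adds the 28-day exclusion. Section 3.5 lists neither, so it is not a complete list of changes. Finally, SAP 12.5 counts only rescue given in the present study, which leaves placebo-period rescue unmentioned there.

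Part of this stands. The row label is uneven, and the silence of Section 3.5 should carry little weight. The rest is weaker. Section 12.5 defines events for its own rescue summaries. The rescue and failure rules in Section 4.3 attach to the Version 2 endpoint, which covers both treatments. The parent-endpoint reading has to set aside the Table 3 title and the full name that the SAP uses elsewhere for that status. The p-value shift shown above rests on invented counts and supposes the relabelling that would first have to be shown.

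**Conclusion.** The concern does not hold as a fault in the analysis. An analyst who follows SAP 4.3 and 10.1.2 together will score both periods by Version 2 and obtain the protocol's comparison of p_F with p_P. What is left is a clerical matter: three names for two statuses, and a reference to Section 4.4 that should read 4.3. No numerical conflict can be shown from the documents. The sensitivity of 1/n per patient rests on an assumed n and an unknown number of affected patients, which may be zero. The conclusion assumes that stable responder in Table 3 is short for the stable platelet response of Section 4.3. That is the most natural reading, though the parent studies' own definitions cannot be checked here. Efficacy is a secondary objective of the study, which limits what is at stake further. Matching the labels in a later revision would do no harm, but the plan does not need it.
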